## 7.2 Timing of Evaluations

Refer to Table 5 above for a summary of the evaluations.

### 7.2.1 Screening Evaluations

#### Informed Consent

After identifying potential patients for the study, written informed consent must be obtained from these patients.

#### HIV Testing

HIV testing will be carried out using a licenced rapid HIV test. HIV positive results will be confirmed by a second licenced rapid HIV test. Discordant results will be confirmed by ELISA.

#### Clinical and Laboratory Evaluations

Patients will have height and weight measured, and blood will be drawn for an AST, ALT, total bilirubin, potassium, alkaline phosphatase, total protein Creatinine clearance, unless results from these tests within the previous 14 days are available. A pregnancy test (using urine sample) is required at every visit if patient is a woman of child-bearing potential.

A chest radiograph will also be taken, unless a chest radiograph done within the previous 14 days is available for review. A sputum sample will be obtained for smear and GeneXpert analysis to ascertain Rifampicin resistance and confirm TB infection. Screening evaluations to determine eligibility must be completed  $\leq 14$  days prior to randomization.

In addition to data being collected on participants who enrol into the study, demographic, clinical, and laboratory data on screening failures will be captured in a Screening Failure Results form and entered into the study database.

### 7.2.2 Baseline, Randomization and On Study Evaluations

Eligibility criteria will be assessed by a study clinician prior to randomization. On-study entry evaluations will occur after randomization. Entry evaluations must be completed no more than 3 days after randomization. When the results of the blood tests and chest radiograph are available, and if the patient meets the enrolment criteria, the site must then randomize each new patients according to Section 5 (Randomization Procedures) above. Note, the result of HIV testing is required for randomization. Baseline evaluations (according to SoE, Table 5) will be completed on the same day of the randomization (unless otherwise stated by the Study PI or study clinician) and patients should start on assigned study therapy as soon as possible after randomization but no more than 3 days following randomization.

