## 4.0 INCLUSION AND EXCLUSION CRITERIA

### 4.1 Inclusion

- 4.1.1 Adults  $\geq$  18 years of age
- 4.1.2 Previous history of anti-TB chemotherapy
- 4.1.3 HIV status: HIV infected and uninfected patients are allowed in the study:
  - 4.1.3.1 All patients must agree to HIV testing to confirm HIV status.
  - 4.1.3.2 Patients already on ARVs will be allowed in the study provided that the ART regimen is not contraindicated with any of the study agents (see 4.2.1 below).
  - 4.1.3.3 HIV infected patients at any CD4 count irrespective of ART commencement and duration will be included in the study
- 4.1.4 Smear positive
- 4.1.5 Rifampicin susceptible as determined by Gene Xpert at screening. Gene Xpert will be used to determine Rifampicin resistance, hence the study team will be made aware of resistance prior to study enrolment.
- 4.1.6 Karnofsky score  $\geq$  70
- 4.1.7 Female candidates of reproductive potential must agree to use two reliable methods of contraception while on study: a barrier method of contraception (condoms or cervical cap) together with another reliable form of contraceptive (condoms with a spermicidal agent, a diaphragm or cervical cap with spermicide, an Intrauterine Device (IUD), or hormone-based contraceptive)
- 4.1.8 A negative pregnancy test
- 4.1.9 Laboratory parameters done at, or  $\leq$  14 days prior to, screening:
  - Haemoglobin level of at least 7.0 g/dL
  - Serum aspartate transaminase (AST) and alanine transaminase (ALT) activity less than 3 times the upper limit of normal
  - Serum total bilirubin level less than 2.5 times upper limit of normal
  - Creatinine clearance (CrCl) level greater than 60 ml/min
  - Platelet count of at least  $50 \times 10^9$  cells/L
  - Serum potassium greater than 3.0 mmol/L

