### 4.2 Exclusion

- 4.2.1 Patients on a Nevirapine (NVP)-containing ART regimen at screening
- 4.2.2 Pregnant or breastfeeding
- 4.2.3 Received an antibiotic active against *M. tuberculosis* in the last 14 days (e.g. fluoroquinolones, macrolides, standard anti-tuberculosis drugs).
- 4.2.4 Patients with known *M. tuberculosis* resistance to any of the study drugs at screening
- 4.2.5 History of prolonged QT syndrome or current or planned therapy with quinidine, procainamide, amiodarone, sotalol, or ziprasidone during the intensive phase of tuberculosis treatment.
- 4.2.6 Known allergies or intolerance to any of the study drugs.

NOTE: All potential participants will undergo screening evaluations to determine eligibility. The site investigator (or designate) will assess eligibility and ensure that the participant meets all of the inclusion criteria.

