## 6.0 STUDY TREATMENT

### 6.1 Regimens, Administration and Duration

Once randomized to either the Control or Intervention arms the study drug is to be self-administered once daily before meals. Treatment should be commenced no more than 3 days after randomization. The Control and Intervention arms will follow the South African National Tuberculosis dosing guidelines for re-treatment cases as closely as possible. All patients will receive pyridoxine 50mg daily whilst in the study.

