3: PK blood samples, in the intervention arm only, will be taken once during the intensive phase of TB treatment at either Week 4 **OR** Month 2 (**PK bloods may be repeated at Month 2 if these were not taken, incorrectly done or incomplete at Week 4 OR at the discretion of the investigator**), and at the end of TB treatment (Month 6)

4: Additional PK samples will be taken at M7 (or the first visit after if Month 7 is missed) in Intervention Arm before and after the ingestion of the single additional dose of Moxifloxacin. This additional PK sample may be deferred to month after TB treatment completion on participants who have TB treatment extended beyond 6 months

5: If PBMCs are not collected at baseline samples may be taken at Week 4 or Month 2

6. End of TB Treatment visit will be conducted within 7 days of completion of TB treatment.

\* Samples will be collected and stored for future susceptibility testing,

\*\*ECG's will be done at baseline, Month 2 and Month 4 and Month 6. ECG's will be performed 2 monthly during treatment with Moxifloxacin

\*\*\*Additional PBMC's will be collected at IRIS and at the time of seroconversion

The study SoE will be followed except when procedures are clinically indicated as not required.

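### A patient with an unrecognised QTcF of 0.50 s or more is eligible, must be randomised and may start moxifloxacin, because no measured QTc limit exists and randomisation does not wait for the baseline ECG

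*Protocol*

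**What the plan says.** **Eligibility.** Protocol 4.2.5 excludes patients with a "History of prolonged QT syndrome or current or planned therapy with quinidine, procainamide, amiodarone, sotalol, or ziprasidone" during the intensive phase. Protocol 4.1.9 adds "Serum potassium greater than 3.0 mmol/L". Neither 4.1 nor 4.2 contains a measured QTc value.

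**Screening.** Under 7.2.1, "Screening evaluations to determine eligibility must be completed" within the 14 days before randomisation. The tests listed there are bloods, pregnancy test, chest radiograph, sputum smear and GeneXpert. The screening column of Table 5 has no ECG either. The Table 5 footnote says that ECGs "will be done at baseline, Month 2 and Month 4 and Month 6".

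**Order around randomisation.** Section 7.2.2 names what must be in hand first: blood results, chest radiograph and HIV result. If the criteria are then met, the site is obliged to randomise. On timing it says:

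- "On-study entry evaluations will occur after randomization. Entry evaluations must be completed no more than 3 days after randomization".
- "Baseline evaluations (according to SoE, Table 5) will be completed on the same day of the randomization", with an exception at the discretion of the principal investigator or clinician.
- "patients should start on assigned study therapy as soon as possible after randomization but no more than 3 days following randomization".

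Section 6.1 adds that "the study drug is to be self-administered once daily before meals", so each day on treatment is one 400 mg moxifloxacin dose in the intervention arm.

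**Action on QTc.** Section 8.5 (QTc Prolongation) grades Fridericia-corrected values. A QTc of 0.50 s or more is Grade 3, as is a QTc above 0.48 s with a rise of at least 0.06 s from baseline. At Grade 3 all study drugs stop and the patient goes to hospital. Section 8.1 calls for an exchange between moxifloxacin and ethambutol on evidence of QT prolongation. It gives no QTc value, no timing and no hold before the first dose.

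**The concern.** The protocol acknowledges that moxifloxacin can prolong QTc, and its own stopping value for an absolute QTc is 0.50 s. One would expect a patient already at that value not to be started on the drug. The entry rules cannot ensure this. History, a short drug list and potassium pick up known or suspected risk, but not prolongation that nobody has measured. The one test that would show it is scheduled for every patient, yet nothing makes it a condition of randomisation or of the first dose.

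This is a matter of patient safety and internal consistency. A smaller consequence concerns grading. If the baseline ECG is recorded after dosing has begun, it may already contain some drug effect. The rise from baseline is then understated, and a patient between 0.48 and 0.50 s could be graded 2 (closer monitoring) instead of 3 (stop all study drugs).

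**Working it through.** **Step 1. Follow one patient through the rules.** Take a patient with a QTcF of 0.50 s, no QT history, none of the listed drugs, and potassium above 3.0 mmol/L.

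| Point in the protocol | What it checks | Result |
|---|---|---|
| 4.1, 4.2 | QT history, five drugs, potassium | Eligible |
| 7.2.1, Table 5 screening column | No ECG | Not detected |
| 7.2.2, results needed first | Bloods, radiograph, HIV | Site must randomise |
| 7.2.2, treatment start | As soon as possible, by day 3 | May be dosed |
| Table 5, Baseline | ECG, no order relative to first dose | Detected when read |
| 8.5, Grade 3 | 0.50 s or more | Stop all study drugs |

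The first limb of Grade 3 is an absolute value. It needs no change from baseline, so this patient meets the stopping rule as soon as an on-treatment trace is read.

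**Step 2. Exposure before the ECG is recorded.** Let randomisation be day 0, *s* the day of first dose (0 to 3) and *e* the day of the ECG (0 to 3). Days on drug before the ECG = max(0, *e* − *s*).

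| First dose | ECG day 0 | ECG day 1 | ECG day 2 | ECG day 3 |
|---|---|---|---|---|
| Day 0 | 0 | 1 | 2 | 3 |
| Day 1 | 0 | 0 | 1 | 2 |
| Day 2 | 0 | 0 | 0 | 1 |
| Day 3 | 0 | 0 | 0 | 0 |

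The first column is the default in 7.2.2, and it gives zero throughout. The other columns need the investigator or clinician exception, or the entry-evaluation window applied to the ECG. The extreme is 3 days: doses on days 0, 1 and 2, plus a fourth if the day 3 dose precedes the ECG, so 1200 to 1600 mg. These figures concern when the trace is recorded. No time for reading it is stated, so they do not bound the exposure before it is read.

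**Step 3. Sense of scale, on assumptions.** The total of 330 in Protocol 9.1 reproduces: 75% against 60%, two-sided 0.05, 80% power and continuity correction give 165 per arm. The point here does not depend on it, except that 165 is the size of the moxifloxacin arm.

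Let *p* be the share with unrecognised QTcF of 0.50 s or more, and *q* the share of those dosed before the ECG is read. The documents give neither. Expected number = 165 × *p* × *q*; chance of at least one = 1 − (1 − *pq*)^165.

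| Assumed *p* | Assumed *q* | Expected patients | Chance of at least one |
|---|---|---|---|
| 0.1% | 10% | 0.0165 | 1.6% |
| 1% | 10% | 0.165 | 15% |
| 1% | 100% | 1.65 | 81% |

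The range is too wide to serve as an estimate.

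**Step 4. Grading, in the exceptional case of a post-dose baseline.** If the recorded baseline already holds *d* seconds of drug effect, the true rise needed for the second Grade 3 limb becomes 0.06 + *d*. For an assumed *d* of 0.005 to 0.015 s, that is 0.065 to 0.075 s.

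Illustration: with a true pre-dose value of 0.425 s and an on-treatment value of 0.487 s, the rise is 0.062 s, Grade 3. With *d* = 0.005 s the recorded baseline is 0.430 s, the apparent rise 0.057 s, and the grade 2.

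**The case against.** The strongest reply is that baseline ordinarily means before treatment. The Baseline column of Table 5 also holds the eligibility check, randomisation, sputum culture and susceptibility, and a baseline culture taken after several doses would not serve its purpose. Section 7.2.2 puts Baseline-column items on the day of randomisation and mentions treatment start afterwards. On this reading, three days of dosing before the ECG comes from loose wording and is not what the plan prescribes. That stands, and it is why the default exposure is taken as about zero and the grading point as minor.

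Safeguards also exist: the history, drug and potassium criteria, an ECG for every patient, the QT rule in 8.1, the graded rules in 8.5, and the investigator's freedom to stop treatment. They narrow the gap to unrecognised prolongation. They do not close it, because each ECG-based rule acts only once a trace has been read, and nothing places that reading before randomisation or the first dose.

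It is also fair to say that 8.5 grades events arising on study, so 0.50 s is not an eligibility limit in the protocol. Using it as one is a choice, but the choice that makes entry agree with the protocol's own absolute stopping value.

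A reader might infer that patients will routinely take moxifloxacin for three days before an ECG, or that three days is the most that can pass before prolongation is noticed. The documents support neither: the default is the same day, and reading time is unspecified.

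**Conclusion.** The point holds as a safety and consistency gap that should be corrected. As written, the rules admit and oblige the site to randomise a patient with unrecognised QTcF of 0.50 s or more, and allow moxifloxacin to be started at a value where the protocol stops all study drugs. This follows from the text of 4.1, 4.2, 7.2.1, 7.2.2 and 8.5 and rests on no outside standard.

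Its size is modest. Exposure before the ECG is recorded is often about zero and at most 3 days within the stated windows. The number of patients cannot be derived from the documents and is probably small; the counts in the working rest wholly on assumed *p* and *q*. A reader might take the 81% as a forecast that an affected patient will be dosed. It is not: it needs 1% prevalence and every affected patient dosed before the trace is read, which fits poorly with the same-day default.

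The effect on the efficacy comparison is negligible, and the sample size of 330 is unaffected.

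**What to change.** 1. In 7.2.2, require the scheduled baseline ECG to be done and read, with Fridericia correction, before the randomisation envelope is opened, and add it to the results that randomisation waits for.
2. In 4.2.5, exclude a measured QTcF of 0.50 s or more, matching the absolute Grade 3 limit in 8.5.
3. As a minor addition in 8.5, state that baseline for the 0.06 s rise means this pre-dose ECG.

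With the first change, exposure before the ECG is read is zero in every cell of the table above.

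No procedure is added, since every patient already has the ECG. The cost is a slightly longer pre-randomisation step and a few extra screening failures. The arm is not known at that point, so the exclusion falls on both: at the assumed 0.1% to 1%, 330 × 0.001 = 0.33 to 330 × 0.01 = 3.3 patients.

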### 7.2.3 Post Entry Evaluations

#### Study visits - intensive phase of therapy

Intervention Arm - study visits Week 4 and Month 2 will be considered as intensive phase

Control Arm - study visits Week 4, Month 2 will be considered as intensive phase

A delay in the time to sputum conversation may result in an extension of the intensive phase.

Regardless of arm, at each study visit for which the patient is in the treatment phase, a sputum sample will be obtained. Sputum induction will be resorted to in the event that the participant is unable to provide a

spontaneous, good quality sputum specimen. Laboratory tests for safety monitoring will also be obtained at study visits during the intensive phase of therapy. Vision testing will be performed at baseline and repeated at Month 2 for Control Arm only. Patients found to have HIV infection will have blood drawn for a CD4 cell count and HIV RNA level at the first study visit after HIV infection is confirmed (as per the study SoE). PBMC samples will be collected if a patient seroconverts whilst on study.

Follow up management of HIV-infected patients will be as per SA HIV guidelines.

#### Study visits – continuation phase of therapy

Intervention arm - study visits Month 3 to Month 6 will be considered as continuation phase.

Control arm - study visits Month 3 to Month 6 will be considered as continuation phase.

Month 4 – Patients will have an assessment for toxicity from the four-drug phase of therapy. This will consist of a symptom-driven examination, and laboratory testing (complete blood count and serum AST, total bilirubin, and serum creatinine). A sputum specimen will be obtained for culture.

Month 4-6–Patients will continue to have study visits monthly during the continuation phase of therapy. Sputum cultures will be obtained at Month 4, Month 5, Month 6 during the continuation phase of therapy. Laboratory testing, other than sputum cultures, will be at the discretion of the principal investigator/study clinician.

#### Pharmacokinetic studies

PK studies will be conducted on a subset of the study population. PK analyses will assess the potential interaction between Moxifloxacin and Rifampicin containing TB treatment in patients with recurrent TB, and to determine the effect of Moxifloxacin and Rifampicin containing TB therapy drug concentrations on TB treatment outcomes.

#### Lipoarabinomannan studies

All participants included in the parent study would be included in the urine LAM sub-study. Participants would provide urine samples at baseline, as well as 2- and 5 months into anti-tubercular therapy. One additional urine sample will be collected at the end of the assigned treatment course for each participant. Each urine sample would then be tested using one rapid urine LAM test strip in a designated laboratory. Once completed, the test card will be discarded and the urine sample will be stored in a freezer for future testing.

#### *7.2.4 Study Visit Window and Unscheduled Visits*

The window period for all scheduled monthly study visits  $\pm 7$  days. Any visit for which a patient attends outside of the specified visit window but not in addition to those required as per the ‘schedule of evaluations’ should be considered as an early/late visit. The assessments which are undertaken as part of an early/late visit should reflect those for the visit which will be or has been missed. Any additional assessments should be undertaken as clinically indicated.

## 7.3 Instructions for Evaluations

### 7.3.1 Sputum smear, culture and susceptibility

At the time points indicated in the SoE, a sputum sample will be collected for AFB smear, mycobacterial culture and susceptibility.

### 7.3.2 Specimen Storage

Specimens for storage will be stored according to timelines stated in the SoE. In addition to the scheduled timelines, samples found to be culture positive at baseline, Month 4 through Month 8 should be stored. In addition, sputum isolates from smear testing will be stored.

### 7.3.3 Complete Physical Exam

A complete physical examination will be performed at screening only and will include at a minimum Karnofsky performance score, vital signs (i.e., temperature, pulse, respiratory rate, and blood pressure), height, weight, and full examination.

### 7.3.4 Targeted Physical Exam

A targeted physical examination will be performed at every study visit from baseline and on subsequent clinically required visits

### 7.3.5 Pregnancy Testing

For women of reproductive potential: The pregnancy test performed at study according to SoE must be negative.

### 7.3.6 PK sample collection

Plasma samples for storage will be drawn at the following time points in the visit schedule:

- Week 4 (Intervention Arm) OR Month 2 (Intervention Arm)
- Month 2 (Control Arm)
- Month 6 (Intervention Arm)
- Month 7 (Intervention Arm) or one month post end of TB treatment

The duration of the intensive phase of TB treatment may increase due to a delay in the time to sputum conversion. If the duration of TB treatment is extended:

- For Month 6 PK blood draw, End of continuation phase TB treatment (Month 6- Intervention Arm) sometimes the PK is not at end of the continuation phase because TB treatment is extended.
- Month 7 PK blood will be completed at the month following the completion of TB treatment.

Participants will be counselled to take their doses of TB treatment at a similar time once daily until the day before their scheduled study visit. The TB treatment dose on the day of the PK study visit will be ingested by participant at the study clinic. Plasma samples will be taken in the study clinic prior to the dose of TB therapy (Intervention Arm) and at specified time points in the course of the study visit. The plasma will be placed on ice and sent to the CAPRISA laboratory to be centrifuged and stored at –80 degrees Celsius for analysis at a later time.

## Pharmacogenetic Studies:

Drug metabolizing enzymes will be assessed to investigate the effect of specific polymorphisms on drug concentrations/pharmacokinetics of moxifloxacin and rifampicin containing TB therapy.

7.3.7 Urine samples for testing and storage will be drawn at the following time points in the visit schedule:

- Baseline (Both Arms)
- Month 2 (Both Arms)
- Month 5 (Both Arms)
- Month 6 (Both Arms) End of TB Treatment (Both Arms)

7.3.8 Procedures for computerized dispensing and cellphone technology: innovative tools to enhance patient adherence, tracking and retention:

Participants who are enrolled and agree to receive a sms within the IMPRESS study will have their cellphone numbers entered onto the Communicate database. Different sms campaigns will be created, using the various cellular phone technology –based functions available:

- An appointment reminder to go out 3 days before the participant is scheduled to present to the clinic, or sooner if visits are scheduled frequently over a short period of time: *“Please do not forget your appointment at the clinic in three days’ time”*
- For those participants who are included in the pharmacokinetic sub-study, a broadcast sms sent out the evening before a scheduled visit, which reminds the patient not to take an evening/morning dose, prior to sample collection at the clinic for pharmacokinetic (PK) study, the next morning: *“Please do not take your TB medication the night or morning before coming to the clinic. Carry TB drugs with you to be taken at the clinic.”*
- A sms to prompt defaulters to return to the clinic: *“You have missed your appointment at the clinic. Please return to the clinic as soon as possible.”*
- An motivational broadcast sms to enhance patient compliance by re-enforcing adherence, programmed to be sent one week after enrolment, and periodically thereafter: at the end of month 1 of treatment and then at the beginning of the continuation phase: *“TB can be cured and the spread of TB stopped if the full course of treatment is taken correctly, so that people can lead fuller, safer and healthier lives.”*

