##### Moxifloxacin:

Moxifloxacin has been shown to be effective in the treatment of tuberculosis and may shorten time to culture conversion, Moxifloxacin has few clinically relevant drug-drug interactions, although a potential drug-drug interaction exists between Rifampicin and Moxifloxacin. Moxifloxacin is not a substrate for the cytochrome P450 enzyme system, the locus of many drug-drug interactions involving Rifampicin. However, Rifampicin also induces the activity of the cytosolic enzymes glucuronosyltransferase and sulphotransferase, and Moxifloxacin is metabolized by glucuronide and sulfate conjugation. As a consequence, Rifampicin may up-regulate the metabolism of Moxifloxacin and result in decreased Moxifloxacin concentrations. One study found that concomitant Rifampicin administration results in 27% decrease in Moxifloxacin AUC. Additional studies are needed to determine whether this difference is clinically relevant. Because Rifampicin is included in all of the treatment regimens in which Moxifloxacin is likely to be used (except those used for treatment of Rifampicin-resistant tuberculosis), it is important that the clinical relevance of this potential interaction be evaluated.

Moxifloxacin is metabolized by glucuronide and sulfate conjugation with the sulfate conjugate (M1) accounting for 38% and the glucuronide conjugate (M2) accounting for 14% of the oral dose. Another protein, P-glycoprotein, plays an important role in absorption, distribution and elimination of xenobiotics and may

affect drug concentrations of Moxifloxacin and Rifampicin containing TB drug therapy. Rifampicin and the quinolones have been reported to be substrates of P-glycoprotein. More than 20 single nucleotide polymorphisms have been identified in the MDR1 gene, and interethnic differences in the frequencies of MDR1 mutations leading to altered P-glycoprotein function are likely to contribute to interethnic differences in drug efficacy and toxicity. Genetic variation in the MDR1, UDP-glucuronosyl transferase and other relevant genotypes of drug metabolizing enzymes may modify Moxifloxacin and Rifampicin containing TB drug concentrations/pharmacokinetic values. Further evaluations among patients with tuberculosis disease are warranted to evaluate clinical relevance and effects on therapeutic outcomes.

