The pharmacokinetic-pharmacodynamic marker that best predicts the efficacy of fluoroquinolones, including Moxifloxacin is the area under the curve (AUC) to MIC ratio. The AUC/MIC ratio has been shown to be a reliable measure of Moxifloxacin activity. AUC/MIC ratio of > 100 has also been demonstrated to be associated with better TB treatment outcomes and greatest bacteriological activity against *Mycobacterium tuberculosis* and a decreased probability of resistance.

There is very limited data on the effects of drug concentrations of the quinolones as part of first line TB drug regimens on TB treatment outcomes. Moxifloxacin has a variable pharmacokinetic profile and a number of covariates including but not limited to body mass index (BMI), co morbidities, disease severity, may affect Moxifloxacin drug concentration. This study will provide valuable information on the contribution of Moxifloxacin drug concentrations as part of a Rifampicin containing TB drug regimen on therapeutic outcomes in patients with recurrent TB.

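### The PK reminder text message and Protocol 7.3.6 give evening dosers conflicting instructions, so on-treatment PK samples fall about 36 h or 12 h after the last dose, against 24 h in morning dosers

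*Protocol*

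**What the plan says.** Three parts of the Protocol govern the dose before an on-treatment PK visit (Week 4 or Month 2, and Month 6, in the Intervention Arm; Month 2 in the Control Arm).

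- **6.1** sets the routine: "the study drug is to be self-administered once daily before meals". No clock time is given.
- **7.3.6** covers the days before sampling: "Participants will be counselled to take their doses of TB treatment at a similar time once daily until the day before their scheduled study visit". On the visit day itself, dosing takes place at the clinic. A sample before that dose is stated for the Intervention Arm only.
- **7.3.8** describes a text sent the evening before the visit, "which reminds the patient not to take an evening/morning dose, prior to sample collection at the clinic for pharmacokinetic (PK) study", with sampling the next morning. The message reads: "Please do not take your TB medication the night or morning before coming to the clinic". It goes only to a subset: "Participants who are enrolled and agree to receive a sms within the IMPRESS study".

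Section 1.5 gives the background to the exposure measure: "The AUC/MIC ratio has been shown to be a reliable measure of Moxifloxacin activity". It also reports one study in which "concomitant Rifampicin administration results in 27% decrease in Moxifloxacin AUC". Ancillary objectives 2.3.2 and 2.3.3 relate drug concentration and PK/PD parameters to outcome and seek the extent of the moxifloxacin–rifampicin interaction.

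**The concern.** On the eve of the visit an evening doser is told by 7.3.6 to take the dose and by 7.3.8 to leave it out. The Protocol foresees evening dosers, since 7.3.8 speaks of withholding either an evening or a morning dose. Nothing moves them to mornings beforehand or sets a target time since the last dose.

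Both off-schedule intervals can therefore occur within the evening dosers. Those who obey the text skip a dose. Those who decline texts, have already dosed when it arrives, or follow the 7.3.6 counselling do not. The carry-over into the sampled interval then depends on dosing habit and on whether the text was received and followed, so the error is not pure noise. At stake is the moxifloxacin exposure that the PK objectives relate to culture conversion and to the rifampicin interaction. In an affected profile the error at 12 h is close in size to the 27% interaction effect under study.

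**Working it through.** The documents state no interval or PK error, so there is no figure of the plan's own to reproduce.

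**Step 1: intervals.** Assumed clock times (not in the documents): clinic dose 08:00, evening dose 20:00, morning dose 08:00.

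| Participant | Last dose | Interval |
|---|---|---|
| Evening doser, obeys text | two evenings before | 8 + 48 − 20 = 36 h |
| Evening doser, follows 7.3.6 or gets no text | evening before | 8 + 24 − 20 = 12 h |
| Morning doser | previous morning | 8 + 24 − 8 = 24 h |

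With clinic dose 07:00–10:00, evening dose 18:00–22:00 and morning dose 06:00–08:00, the bands are 33–40 h, 9–16 h and 23–28 h. They do not overlap.

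**Step 2: pre-dose level.** With first-order decay and half-life h, the ratio to the 24 h level is 2^(−12/h) at 36 h and 2^(12/h) at 12 h. For an assumed h of 6–14 h this is 0.25–0.55 at 36 h and 4.0–1.8 at 12 h.

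**Step 3: AUC0-24 after the clinic dose.** One-compartment model at steady state on 24 h dosing, assumed absorption rate ka = 2/h, last interval g. The share of a single dose's AUC still to come at time t is

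T(t) = (ka·e^(−kt) − k·e^(−ka·t)) / (ka − k).

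Summing over past doses telescopes, and the ratio to the 24 h case is

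R(g) = 1 − T(24) + T(g).

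Assumed moxifloxacin half-life without rifampicin: 8–15 h, with k = ln 2/h. To reflect rifampicin, k is divided by 0.73, from the 27% AUC fall in section 1.5. Both versions are shown.

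Worked case, h = 12 h with rifampicin: k = 0.0578/0.73 = 0.0791; T(12) = 0.403, T(24) = 0.156, T(36) = 0.060. Then R(36) = 1 − 0.156 + 0.060 = 0.904 and R(12) = 1 − 0.156 + 0.403 = 1.247.

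| Half-life (h) | R(36), k/0.73 | R(12), k/0.73 | R(36), k | R(12), k |
|---|---|---|---|---|
| 8 | 0.953 | 1.194 | 0.916 | 1.239 |
| 10 | 0.927 | 1.228 | 0.889 | 1.255 |
| 12 | 0.904 | 1.247 | 0.871 | 1.257 |
| 15 | 0.880 | 1.257 | 0.856 | 1.250 |

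So the uncorrected AUC0-24 is 5–14% low at 36 h and 19–26% high at 12 h. With clinic dose 08:00–10:00 and evening dose 18:00–22:00 (gaps 34–40 h or 10–16 h), it is 4–18% low or 10–32% high. For a drug with an assumed half-life of 2–4 h it is 0–1.5% low at 36 h and 2–12% high at 12 h.

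**Step 4: net direction.** If a share p of evening dosers is at 12 h, their mean bias is zero at p = (1 − R(36))/(R(12) − R(36)). For the worked case, 0.096/0.343 ≈ 0.28; over the table, 0.19–0.37. At a 50/50 split the mean is 5–8% high. The documents do not give p.

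**Step 5: overall mean.** If 10–50% of profiles come from evening dosers (assumed):
- all at 36 h: from 0.10 × 4.7% ≈ 0.5% low to 0.50 × 14.4% = 7.2% low;
- all at 12 h: from 0.10 × 19.4% ≈ 1.9% high to 0.50 × 25.7% ≈ 12.9% high.

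**Step 6: can analysis repair it?** The corrected value AUC0-24 − C0/k + C24/k recovers the single-dose AUC exactly at 12, 24 and 36 h when k is known. If k is 20% wrong, at most 6.4% error remains at 12 h and 3.6% at 36 h.

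**Step 7: morning doses needed after a switch.** Worst case over the table: one dose leaves AUC within 8.3% and the pre-dose level within 25%; two doses, 2.7% and 8.1%; three doses, 0.9% and 2.7%; four doses, 0.3% and 0.9%.

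**The case against.** **An uncorrected AUC0-24 is nowhere stated as the planned measure.** AUC/MIC appears as background, no 24 h sample is stated, and a population model fitted to actual dose times would carry no such error. This stands as a limit. The percentages describe what happens if the interval is ignored, and the PK analysis plan and PK CRF are not among the documents. For the same reason the correction in step 6 may need an extrapolated C24, and its residuals do not cover that.

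**The size rests on assumptions.** Half-life, absorption, clock times and the share of evening dosers are all assumed. Since every on-treatment profile is under rifampicin, the k/0.73 columns arguably fit better; they give 5–12% low at 36 h and leave 19–26% high at 12 h. That narrows one end only.

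**The two sections can be read as agreeing.** If 7.3.6 excludes the day before the visit, evening dosers are at 36 h under both texts. But morning dosers are then at 48 h, so intervals still differ by habit. The reading is also less natural, because the next sentence of 7.3.6 already deals with the visit-day dose.

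**The text is called a reminder**, which suggests earlier face-to-face instruction and fewer participants at 12 h. That is possible, but the only counselling described is that in 7.3.6, which leads to 12 h.

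**Three days of morning dosing is more than needed**, since two already bring AUC within 2.7%. This is a fair trade-off to raise. The third dose mainly tightens the pre-dose level, from 8.1% to 2.7%.

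**Conclusion.** The concern holds, and it is minor. The conflict is in the text itself, and the unequal intervals follow from it under either reading of 7.3.6. The error in AUC is conditional on an analysis that ignores time since last dose, and on the assumed half-lives and clock times above. Its net direction in evening dosers cannot be determined from the documents. Control Arm profiles are the harder ones to correct, because no pre-dose sample is stated for that arm.

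The reach is small: ancillary PK objectives, a PK subset, and an unknown number of evening dosers. The Month 7 single-dose sampling is off treatment and is not affected. Primary and secondary endpoints and the sample size are untouched, and a skipped dose is made up under 8.2.1. Confidence is medium.

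**What to change.** 1. Counsel PK sub-study participants to dose in the morning for at least 3 days before each on-treatment PK visit.
2. Change the text message to say only that the dose due on the morning of the visit should be brought to the clinic and taken there. Word 7.3.6 the same way.
3. Record the date and clock time of the last two doses, if the PK CRF does not already, and use actual dose times and the pre-dose level in the PK analysis.
4. Keep off-interval profiles in the main PK analysis. At most, add a sensitivity summary without them.

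Simply aligning the text with 7.3.6 is not enough. It would leave evening dosers at 12 h, where the AUC error is larger.

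The cost is one message template, one sentence in 7.3.6, a small counselling burden and up to two CRF fields. Evening dosers have one irregular interval (about 12 h or 36 h) when they switch, at least 3 days before the visit; if it is 36 h, the omitted dose is made up under 8.2.1. No visits or samples are added and no data are discarded.
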